## **Appendix F Diabetic ketoacidosis**

### **Recognizing diabetic ketoacidosis**

Diabetic ketoacidosis, including atypical (euglycemic) DKA, is the most serious emergency in patients with T1D and T2D. Common precipitating factors include infections, intercurrent illnesses, psychological stress and noncompliance with insulin therapy. Clinical features of DKA at presentation can be nonspecific; however most patients complain of polydipsia and polyuria for several days before onset of DKA. Symptoms of DKA include rapid weight loss, nausea or vomiting, stomach pain, excessive thirst, fast and deep breathing, confusion, unusual sleepiness or tiredness, a sweet smell to the breath, a sweet or metallic taste in the mouth, or a different odor to urine or sweat (55).

It is possible that GI or other AEs occurring with sotagliflozin may mask presenting symptoms of DKA. Because sotagliflozin lowers blood glucose by insulin independent SGLT1 and SGLT2 inhibition, it is possible for DKA to be present with normal or low blood glucose. Therefore, the Investigator must still consider a DKA event even if blood glucose is low or normal.

More information can be found in the sotagliflozin IB.

If DKA is suspected or confirmed, study treatment should be stopped immediately and should not be re-started unless another cause for the ketoacidosis is identified and resolved.

Caution should be exercised in patients with risk factors for ketoacidosis and patients should be informed of the risk factors. These include low reserve of insulin-secreting cells, conditions that restrict food intake or can lead to severe dehydration, a sudden reduction in insulin or an increased requirement for insulin due to illness, surgery or alcohol abuse.

In addition, IMP administration should be stopped in patients in hospital for major surgical procedures or due to serious illness.

Whenever AE data is collected or the patient reports DKA or intercurrent illness (including infections), generalized weakness, increased weight loss, GI symptoms including nausea, vomiting, or abdominal pain or other symptoms or signs that the Investigator believes may be consistent with DKA, the site will determine if an assessment for DKA, such as assessing blood BHB, is appropriate. If BHB or other laboratory testing confirms the presence of metabolic acidosis, then the "Possible DKA" e-CRF will be completed.

### **Patient communication cards will be printed with the following:**

"If you have any of these symptoms on the list, then contact your study site immediately for assistance with managing your diabetes:

- Inability to maintain oral intake
- Generalized weakness

[figure not shown]
[figure not shown]
[figure not shown]
- Abdominal (belly) pain
- Increased weight loss
- Fever
- Frequent urination, including at night
- Fruity-scented breath
- Confusion
- Acute illness
- Consistently elevated blood glucose
- Feeling very thirsty or drinking a lot
- Nausea or vomiting
- Having trouble thinking clearly or feeling tired.

It is possible to have DKA even if your blood glucose is not elevated. Regardless of your blood glucose level, if you have any of these symptoms on the list, then contact your study site regarding the need to be evaluated for possible DKA, which will include specific blood testing. If your study site is closed and your study doctor is not available, go to the nearest emergency room for evaluation.

If you are scheduled for a procedure or surgery that requires you to not take any food or liquids, please contact your study doctor for instructions on continuing study drug. In such cases your study doctor may advise you NOT to take your study drug from the day prior to the procedure or surgery until after the procedure or surgery is complete, and you are taking food and liquids as you normally do.”

## EFC15156 16.1.1 Amended protocol 01

## LIST OF ABBREVIATIONS AND DEFINITION OF TERMS

AE	Adverse event
AESI	Adverse events of special interest
BMI	Body mass index
CV	Cardiovascular
DAOH	Days alive and out of hospital
eGFR	Estimated glomerular filtration rate
EOSI	Events of special interest
HbA1c	Hemoglobin A1c
HF	Heart failure
HHF	Hospitalization for heart failure
IMP	Investigational medicinal product
ITT	Intent-to-treat
LVEF	Left ventricular ejection fraction
MI	Myocardial infarction
PDAOH	Percent days alive and out of hospital
PT	Preferred term
SBP	Systolic blood pressure
WHF	Worsening heart failure

# 1 OVERVIEW AND INVESTIGATIONAL PLAN

## 1.1 BACKGROUND

SOLOIST is a Phase 3, multicenter, randomized, double-blind, placebo-controlled, parallel group, stratified study of sotagliflozin for the treatment of patients with worsening heart failure.

After screening, patients who met all eligibility criteria were centrally randomized via in a 1:1 ratio to sotagliflozin or placebo at randomization visit. Randomization was stratified by baseline left ventricular ejection fraction (LVEF) (LVEF<50% and LVEF≥50%) and region (North America, Latin America, Western Europe, Eastern Europe, and rest of the world).

The original plan was to randomize approximately 4000 patients. However, SOLOIST enrollment was closed in March 2020 before meeting this objective.

A recent publication in the Journal of the American College of Cardiology discussed how clinical trials and programs have been disrupted by the COVID-19 pandemic. It provided the sotagliflozin program as an example where clinical trials have been prematurely terminated. Recommendations included careful consideration of statistical issues relating to potential loss of power, increased variability in data, and challenges in adjudication of events. Similarly, the FDA has issued guidance specific to COVID-19 recognizing the potential for disruption of clinical trials and identifying some of the data and statistical issues that need to be addressed by investigators and sponsors.

This plan describes statistical efficacy analyses to be conducted by an independent academic statistician and separately verified by the Lexicon statistical team. It addresses issues related to the early termination of SOLOIST. These issues have been reviewed and the recommended steps have been chosen in a blinded fashion without the use of any unblinded interim analysis.

The termination of enrollment and follow-up of SOLOIST did not allow enough time to amend the study protocol. Changes to the intended analysis plan are reflected in this document, rather than the protocol, and this plan takes precedence where there are differences between the two documents.

The key efficacy focus is on total (first and potentially subsequent) investigator-reported events. This focus captures the impact of treatment in actual practice. Recurrent hospitalization for heart failure, as recognized and treated by the medical community, is very frequent and has a significant clinical and societal impact. In contrast, a standard assessment of time to a first event may not capture the totality of the effects of treatment. The number of total investigator-reported events in SOLOIST is a measure of high clinical relevance, and consequently is appropriate to summarize the effects of sotagliflozin in SOLOIST.

While larger studies have been performed on SGLT inhibition in heart failure, they have not been performed in an acute setting of worsening heart failure. In contrast, sotagliflozin has been initiated at a time when patients urgently need additional treatment, and this raises important

questions about safety and efficacy of SGLT inhibitor when initiated in the hospital or immediately after discharge. Furthermore, sotagliflozin inhibits both SGLT1 and SGLT2, in contrast to approved SGLT inhibitors that only affect SGLT2. A genomic study of reduced function variations in the SGLT1 gene found these variations were associated with less congestive heart failure and lower mortality. The efficacy of sotagliflozin may be therefore associated with efficacy and safety profiles that differ from those of approved SGLT2 inhibitors.

## 1.2 OBJECTIVES

### 1.2.1 Primary objective

The primary objective of this analysis is to compare the effect of sotagliflozin to placebo on the total occurrences of cardiovascular (CV) death, hospitalization for heart failure (HHF), and urgent visit for heart failure (HF) in hemodynamically stable patients after admission for worsening heart failure (WHF).

### 1.2.2 Secondary objectives

The secondary objectives of the study are to compare the effects of sotagliflozin to placebo on:

- The total occurrences of HHF and urgent visit for HF
- The occurrence of CV death
- The occurrence of all-cause mortality
- The total occurrences of CV death, HHF, urgent visit for HF, non-fatal myocardial infarction (MI), and non-fatal stroke
- Change in KCCQ-12 score
- Change in estimated glomerular filtration rate (eGFR)

[figure not shown]
## 1.3 DETERMINATION OF SAMPLE SIZE

The originally assumed sample size of 4,000 patients was based on a hazard ratio of 0.81 and the desire to examine effects in both the overall population and those with LVEF>50%. Given the early termination of SOLOIST, the study is not powered for these assumptions. However, an examination of efficacy is relevant because hazard ratios less than 0.81 have been reported with SGLT inhibition in stable heart failure, the potential for efficacy may differ in the setting of acute worsening of heart failure (where efficacy has not been examined to date), and the profile of sotagliflozin (with gastrointestinal SGLT1 inhibition in addition to SGLT2 inhibition) may differ from that of selective SGLT2 inhibitors. These analyses are conducted without any new sample size calculations.

## 1.4 STUDY PLAN

The following figure presents graphically the study design. Of note, the population of SOLOIST is described as one with T2D. While an amendment to SOLOIST allowed the enrollment of

patients without T2D who had reduced ejection fraction, few such patients were enrolled. The primary endpoint will be examined for all patients regardless of diagnosis of T2D:

ED = Emergency Department; FU = Follow-up; HF = heart failure; IMP = investigational medicinal product; T2D = type 2 diabetes; R = Randomization; V = visit; WHF = worsening heart failure; Wk = Week.

## 2 STATISTICAL AND ANALYTICAL PROCEDURES

### 2.1 ANALYSIS ENDPOINTS

#### 2.1.1 Demographic and baseline characteristics

Baseline eGFR, hemoglobin A1c (HbA1c), and other laboratory parameter values for each patient are defined as the value assessed by the central laboratory at randomization.

For the remaining parameters, baseline is defined as the last available value before the first dose of double-blind investigational medicinal product (IMP) or the last available value on or before the day of randomization for patients who were randomized but never exposed to IMP.

#### *Demographic characteristics*

Key demographic variables include:

- Age (years)
- Sex (male, female)
- Race (Asian, Black or African American, White, Other)
- Region (North America, Latin America, Western Europe, Eastern Europe, and rest of world)

#### *Medical history*

The patient's medical/surgical history was collected and coded using the version of Medical Dictionary for Regulatory Activities (MedDRA) currently in effect at the time of database lock.

#### *Medical history of specific interest includes:*

- Diabetes history information
- Type 2 diabetes (yes/no)
- Heart failure history:
  - Principle cause of heart failure (ischemic, nonischemic, unknown)
  - Patient admitted for HF at least one time prior to the index event (yes/no)
  - Patient's NYHA class prior to index event (approximately 1 months prior to index event) (Class I, II, III, IV, and undetermined)
- Atrial fibrillation

#### *Disease characteristics at baseline*

- LVEF (%)
- LVEF category (<50%, ≥50%)
- eGFR (mL/min/1.7m^2)
- % of patients with eGFR category <60 mL/min/1.7m^2
- HbA1c (%)

***Other characteristics at baseline***

- Body mass index (BMI) (kg/m^2)
- Systolic blood pressure (SBP) (mmHg)
- Heart rate (beats/min)
- NT-proBNP (pg/ml)

**2.1.2 Baseline medications and devices**

- Baseline medications are those with a start date prior to randomization (or a missing start date) and an end date after randomization or no end date during the study (use classified as ongoing)

The numbers and proportions by treatment group of the following medications and devices of special interest will be summarized:

*Heart failure medications*

Diuretic, ACE inhibitor, ARB, Sacubitril–valsartan, Beta-blocker, Mineralocorticoid receptor antagonist, Digitalis

*Diabetes medications*

Biguanide, Sulfonylurea, DPP-4 inhibitor, GLP-1 receptor agonist, Insulin

*Heart failure device*

Implementation status (yes/no) of ICD/CRT

**2.1.3 Efficacy endpoints**

Efficacy endpoint events with onset date prior to randomization will not be included in efficacy analysis and instead will be treated as pre-treatment adverse events.

In the analyses of time-to-event efficacy endpoints:

- Deaths not included among the events in the endpoint will be treated as competing events;
- Patients alive at the end of the study will be right censored on the date they were last known to be alive;
- Event types and dates included in the analyses will be those as reported by the investigators; and
- In the case where the exact date of occurrence of an event is not known (the day, month, and/or year are missing), the date will be imputed as described in Appendix .

### ***2.1.3.1 Primary efficacy endpoint***

The primary endpoint is the number of total occurrences (first and potentially subsequent) of the following events: CV death, HHF, and urgent HF visit after randomization

### ***2.1.3.2 Secondary efficacy endpoints***

- Total occurrences (first and potentially subsequent) of HHF and urgent HF visits
- Time from randomization to occurrence of CV death
- Total occurrences (first and potentially subsequent) of CV death, HHF, non-fatal myocardial infarction, and non-fatal stroke
- Total occurrences (first and potentially subsequent) of HHF, urgent HF visit, CV death, and HF while hospitalized
- Time from randomization to all-cause mortality
- Change in KCCQ-12 scores from baseline to Month 4
- Rate of decline in eGFR after Week 4 (mL/min/1.73m^2/year) to the end of the study

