- i All laboratory assessments including serum chemistry (sodium, potassium, chloride, carbon dioxide, Blood urea nitrogen, creatinine, eGFR, glucose, alanine aminotransferase, aspartate aminotransferase, total bilirubin, alkaline phosphatase and total protein) and hematology completed at Screening (Visit 1) are to be performed at Site Local Laboratory. If sites are unable to perform laboratory tests locally, the tests can be done by central laboratory. At Randomization and at subsequent visits, laboratory assessments (with the exception of digoxin) are to be performed using central laboratory. At the Randomization Visit (Visit 2), laboratory samples will be collected prior to first dose of double-blind IMP. If the laboratory assessments were done as standard of care, the most recent results collected after the Index event may be used to formally screen the patients. However serum pregnancy testing must be collected at Screening.
- j Blood samples for BNP or NT-proBNP should be collected at screening via a local laboratory, if not collected earlier following the specific Index event. After Visit 1 blood samples for NT-proBNP will be collected via a central laboratory.
- k After Month 4 (Visit 6), HbA1c will be performed at Month 8 (Visit 7), Month 12 (Visit 8), Month 16 (Visit 9), Month 20 (Visit 10), and Month 24 (Visit 11).
- l Sotagliflozin/metabolite levels may be analyzed via routine blood samples collected throughout the study, eGFR will be measured at the follow-up visit after discontinuation of study treatment.
- m Serum pregnancy testing only at Screening (Visit 1); urine pregnancy testing subsequently. Any positive urine test results must be confirmed based on serum pregnancy test. The Investigator may perform additional tests at their discretion or at frequency specified by local regulations. For women of non-productive potential ([Appendix A](#)), FSH and/or estradiol levels should be tested in case the definition of postmenopausal or premenopausal can't be satisfied, eg, no medical document of hysterectomy or cessation of menses without an alternative medical cause is <12 months.

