In Study LX4211.1 202 DM (40) sotagliflozin induced a dose-dependent increase of hematocrit, albumin, and hemoglobin. The mean change (standard deviation [SD]) in hematocrit from Baseline to Week 12 was 0.9% (2.52), 2.0% (2.47), and 1.9% (2.78) in patients receiving sotagliflozin 200 mg qd, 200 mg bid and 400 mg qd, respectively versus -0.5 (2.98) % in the placebo arm. The mean change (SD) in albumin from Baseline to Week 12 was 0.0 (0.279), 0.09 (0.243) and 0.12 (0.242) g/dL in patients receiving sotagliflozin 200 mg qd, 200 mg bid and 400 mg qd, respectively versus (0.273) -0.04 g/dL in the placebo arm. The mean change (SD) in hemoglobin from Baseline to Week 12 was 0.29 (0.775), 0.55 (0.688) and 0.60 (0.820) g/dL in patients receiving sotagliflozin 200 mg qd, 200 mg bid and 400 mg qd, respectively versus -0.19 (1.084) g/dL in the placebo arm. In addition, in the same study, a prespecified sub-analysis of patients with a Baseline BP  $\geq$ 130 mmHg showed that systolic BP decreased by 7 and 14 mmHg (placebo-subtracted), respectively, in the 200 mg qd and 400 mg qd groups.

Therefore, given the observed higher efficacy of the 400 mg dose on glycemic control, hemoconcentration, and BP reduction, and given the potential benefit of these changes on cardiovascular outcomes, the dose of 400 mg was chosen as the proposed maintenance dose for the study.

Sotagliflozin induces an acute, but modest, decrease in estimated glomerular filtration rate (eGFR). Since the study population includes patients at increased risk of acute kidney injury (ie, patients with moderately impaired renal function), study treatment will begin with the low dose of sotagliflozin (200 mg qd) and will be increased to the maintenance dose of 400 mg qd, once tolerability of the low dose has been established by the Investigator.

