### **6.1.3 Post-treatment period**

Patients still taking the IMP at the time of the Study Closeout Visit (ie, who have not prematurely permanently discontinued IMP) will have their final study visit (Follow-up Visit) 14 days ( $\pm 4$  days) after their Study Closeout Visit.

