## **6.2 DURATION OF STUDY PARTICIPATION**

### **6.2.1 Duration of study participation for each patient**

All patients will participate in a Screening period of up to 14 days. The study observation period starts at Randomization and lasts until the end of the study (the last study visit [eg, Follow-up Visit for patients who complete study treatment per protocol, or Study Closeout Visit for patients who prematurely permanently discontinue study treatment] of patient). The study is event-driven, therefore the duration will be determined as described in [Section 6.1.2](#).

The estimated study duration will be approximately 3 to 32 months, assuming approximately 29 months of recruitment, and approximately 3 months of follow-up after the last patient is randomized.

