#### **10.1.5.1 Follow-Up Visit**

Patients who have attended a pEOT Visit do not need to attend this Visit. The following procedures/assessments will be performed at this Visit:

- Vital signs (sitting BP, heart rate)
- Abbreviated physical examination, including lower extremities
- Measurement of eGFR
- IRT contact
- AEs, including SAEs/AESIs/EOSIs (including severe hypoglycemia) and endpoint events (if any) are collected (if a renal endpoint relating to a reduction in eGFR is suspected, see [Section 9.1.2.1](#))

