#### ***2.4.4.2 Analyses of secondary efficacy endpoints***

Methods for controlling the overall type-I error rate when testing the secondary efficacy endpoints are described in Section 2.4.4.3 *Multiplicity issues*.

Time-to-event secondary efficacy endpoints will be analyzed using the same statistical methodology as for the primary endpoint. Deaths that are not part of a given endpoint will be treated as competing events.

As with the primary endpoint, the absolute risk reduction (ARR) of time-to-event secondary endpoints will be estimated by the difference between treatment groups in the number of events per 100 patient-years of follow-up. For those secondary endpoints which are a composite of events, results will be provided for both the overall composite and its individual components.

Absolute change in KCCQ-12 scores from baseline to Month 4 will be analyzed by analysis of covariance (ANCOVA) with treatment group as factor and baseline KCCQ-12 score and randomization stratification factors as covariates. The last available post-baseline score will be

carried forward to Month 4 if the patient is alive at Month 4 but the Month 4 value is missing. For patients who die, a worst score (0) will be imputed for the clinical summary score at all subsequent scheduled visits after the date of death where the clinical summary score would have been assessed.

The rate of decline in eGFR observed over time will be analyzed by repeated-measures mixed-effects models with absolute change in eGFR from baseline as the outcome, a random effect for intercept, and fixed effects for treatment, baseline value, and time. An additional model will be developed with an interaction between treatment and time. The variance-covariance matrix will be specified to be unstructured.

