**2.5.4 Windows for time points**

Data analyzed by time point (laboratory safety data, vital signs, KCCQ-12) will be summarized using the time windows given the table below. These time windows will be applicable for all analyses, and they are defined to provide more homogeneous data for time point-specific analyses that the visit windows specified in the protocol. If multiple values of a parameter are available in a time window, the last will be used in a given analysis.

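### The eGFR slope has no upper limit on samples, so the off-drug Follow-up Visit value can enter and, if the acute fall reverses, tilt the slope towards sotagliflozin

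*SAP*

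**What the plan says.** **Endpoint.** SAP 2.1.3.2 defines it as "Rate of decline in eGFR after Week 4 (mL/min/1.73m 2 /year) to the end of the study". The start is fixed; the end is not defined for this endpoint anywhere in the SAP.

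**Study end.** Protocol 6.2.1 equates it with the last study visit, giving as one case the "Follow-up Visit for patients who complete study treatment per protocol". Patients still on drug at close-out "will have their final study visit (Follow-up Visit) 14 days" (± 4) later (Protocol 6.1.3). SAP Appendix A also takes the later of close-out and final follow-up as the last study visit when censoring the primary endpoint.

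**Off-drug sample.** Footnote l of the flow chart (Protocol 1.2) says "eGFR will be measured at the follow-up visit after discontinuation of study treatment". Protocol 10.1.5.1 lists "Measurement of eGFR" among the procedures at that visit.

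**Drug effect.** Protocol 4.4.1 describes an acute but modest eGFR decrease on sotagliflozin. It gives no size and does not say whether the decrease reverses.

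**Model.** SAP 2.4.4.2 specifies a mixed model for change from baseline with a random intercept and fixed effects for treatment, baseline and time. It then adds: "An additional model will be developed with an interaction between treatment and time". It restricts neither visits nor on-drug status, and it does not say which model is tested.

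**Windows.** SAP 2.5.4 says: "If multiple values of a parameter are available in a time window, the last will be used in a given analysis". No on-drug condition is attached.

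**The concern.** Starting the slope after Week 4 is meant to leave the acute fall out. That works only if the last point is taken in the same treatment state as the first. If the series starts on drug and ends off drug, any reversal of the acute fall appears as an upward step at the final sample, in the sotagliflozin arm only. A linear slope reads that step as slower decline.

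The endpoint is inside the type I error sequence (SAP 2.4.4.3). SAP Appendix D says change in eGFR was added because, with the follow-up available, it is more sensitive than the composite renal endpoint. Shorter follow-up also makes a given step count for more per year.

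There is a second gap. The first model in SAP 2.4.4.2 has one common time effect, so it contains no difference in slope between arms. Only the additional model does. The endpoint is a rate of decline, yet the plan does not say that the model which measures a difference in that rate is the one tested.

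**Working it through.** The documents give no SD, target effect or power for the eGFR slope, so there is no planned figure to reproduce. The check asks how far the treatment-by-time coefficient moves when the true slope difference is zero and the Follow-up value carries a step of 1 mL/min/1.73 m² in the sotagliflozin arm.

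**From the documents**
- Visits at Day 29, Day 113, then every 4 months, with close-out at T (Protocol 1.2).
- Follow-up at T + 10 to 18 days (Protocol 6.1.3).
- Planned follow-up of 3–32 months (Protocol 6.2.1).
- Random-intercept model (SAP 2.4.4.2).

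**Assumed**
- Step of 1 unit; placebo step 0.
- Follow-up attendance 100%, 40% or 10%.
- T uniform over 3–32 months, or over 3–18 or 3–12 months to reflect early termination.
- Within-patient correlation ρ = 0.6.
- Everyone on drug to close-out, unless stated.

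**By hand, one patient.** For a straight line fitted within a patient, a unit step on the last sample moves the slope by (t_last − t̄) / Σ(t − t̄)². Take close-out at Day 365, with samples at Days 29, 113, 225, 337, 365 and 379:
- t̄ = 1448/6 = 241.3
- Σ(t − t̄)² = 105,219
- t_last − t̄ = 137.7
- shift = 137.7/105,219 × 365.25 = +0.48 per year

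Without the Day 29 sample, t̄ = 283.8 and the shift is 95.2/51,116.8 × 365.25 = +0.68 per year.

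**Whole trial.** The pooled estimate is b = (ΣX′V⁻¹X)⁻¹ ΣX′V⁻¹y, with V = (1 − ρ)I + ρJ, over 12,000 simulated sotagliflozin patients per scenario. Shift in slope difference, mL/min/1.73 m²/year per 1 mL/min/1.73 m² reversed:

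| Follow-up (months) | 100% attend | 40% | 10% |
|---|---|---|---|
| 3–32 | +0.22 | +0.10 | +0.03 |
| 3–18 | +0.46 | +0.22 | +0.06 |
| 3–12 | +0.80 | +0.40 | +0.11 |

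Repeat runs at 100% gave +0.21, +0.45 to +0.46 and +0.75 to +0.77. For ρ from 0.4 to 0.8, with or without the Week 4 sample, the 100% column ranges over 0.21–0.26, 0.44–0.60 and 0.77–1.17. With no reversal, or with the Follow-up sample left out, the shift is 0.

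**With the SAP 2.5.4 windows applied.** Windows of ±28 days on visits 112 days apart cover 57 of every 112 days, so about half of Follow-up values drop out. In about 38%, 39% and 43% of patients with both values, however, the Follow-up value replaces the on-drug close-out value. The shift at 100% / 40% / 10% attendance becomes:
- 3–32 months: +0.17 / +0.07 / +0.02
- 3–18 months: +0.47 / +0.20 / +0.05
- 3–12 months: +0.88 / +0.39 / +0.10

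**Model without interaction.** No slope difference exists in it. Its average treatment difference moves by +0.16, +0.20 and +0.24 mL/min/1.73 m² at 100% attendance, and by about +0.02 at 10%.

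**Slope ended at close-out.** The shift is 0 if nobody stops early. If 10% / 20% stop early and keep attending, their off-drug values leave +0.05 / +0.10 (3–32 months), +0.09 / +0.18 (3–18) and +0.14 / +0.28 (3–12).

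**The case against.** **An opposing step exists.** A first up-titration to 400 mg may come at Month 1, 4 or 8 (Protocol 8.1.1.1), inside the slope period. If the acute fall depends on dose, that pushes the slope against sotagliflozin. In the same model, an extra 1 mL/min/1.73 m² fall in 30% of patients gives −0.15 / −0.29 / −0.40 per year for the three follow-up ranges; 0.5 in 20% gives −0.05 / −0.10 / −0.14. This stands: the net bias could be smaller or of the other sign. But it is a separate assumed step, and two unplanned steps that may partly cancel are no reason to keep one of them.

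**Reversal is not documented, and Follow-up samples may be few.** Both true. Close-out through other means of contact counts as completion (SAP 2.2), and sites were told to finish end-of-study contacts (SAP 2.4.4.4). Hence the 10% column.

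**The protocol supplied is Amended Protocol 01.** SAP 1.4 and Appendix D refer to an Amendment 2 that is not supplied, and the visit or its tests could have changed. The SAP takes precedence over the protocol (SAP 1.1), but it is silent on this point.

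**The windows limit samples.** They do so by timing only. They do not screen out off-drug values, and the shift survives them.

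**The calculation is simpler than the plan.** It uses one constant correlation, whereas SAP 2.4.4.2 asks for an unstructured matrix. Varying the correlation changed little.

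**Ending at close-out is a hybrid.** It removes completers' off-drug value and keeps early discontinuers' values. It also presumes patients were still on drug at close-out, which the documents do not confirm after early termination. The residual is shown above.

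**Importance.** The endpoint is last of seven in a fixed sequence. That limits the consequence, not the correctness.

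**Conclusion.** The concern holds. Read with Protocol 6.2.1, the slope period takes in an off-drug eGFR for treatment completers, and nothing in the SAP excludes it. If any of the acute fall reverses, that sample shifts the treatment-by-time slope towards sotagliflozin by +0.03 to +0.80 mL/min/1.73 m²/year per 1 mL/min/1.73 m² reversed, depending on attendance and length of follow-up. The size rests on assumed reversal, attendance and follow-up; the direction of this one step does not. Whether the shift would matter clinically cannot be judged, because the plan gives no target effect for the slope.

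The formal consequence is narrow. The test is reached only if every earlier endpoint in the sequence succeeds, and the slope test is affected only if the interaction model is the one used. The failure to name the tested model needs correcting whether or not the fall reverses. Neither gap threatens the primary result; both are cheap to close.

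**What to change.** - **SAP 2.1.3.2 and 2.4.4.2:** keep the ITT slope as the main analysis, but end it at the Study Closeout Visit and exclude the Follow-up Visit eGFR by visit label.
- **SAP 2.4.4.2:** state that the model with the treatment-by-time interaction is the one tested in the sequence.
- **SAP 2.5.4:** give close-out and Follow-up separate labels, so that the last-value rule cannot replace the close-out value.
- **Sensitivity analysis:** add an on-treatment slope through last dose plus 10 days, the limit already used in SAP 2.1.4. Note two weaknesses. It drops later values from patients who stopped for renal decline (Protocol 10.3.3), so selection is tied to the outcome. It also keeps off-drug values during temporary interruptions (Protocol 10.3.1); with 10–20% of patients interrupted once for 30–90 days, the effect on the slope was 0.01 or less.
- **Separate report:** give change from baseline to the off-drug Follow-up Visit on its own.

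The cost is SAP wording and at most one eGFR value per completer. Early discontinuers' off-drug values remain in the ITT slope (Protocol 10.3.4), so some shift is left, as shown in the working.
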